### 6.3. Handling of Special Measurement Values

For BCVA, Finger Counts, Hand Motion, Light Perception, or No Light Perception will be set to 0 letter in the analysis.

For measures determined by SD-OCT and FA, “Ungradable” will be treated as missing data.

For M-CHARTS™, any VM and HM with “Unmeasurable” in Type I and Type B will be set to 2 and 2.4, respectively.

#### **6.4. Multi-Center Studies**

This is a multi-center study enrolling subjects from up to 14 sites. No pooling algorithm will be applied.

#### **6.5. Multiple Comparisons / Multiplicity**

Multiplicity adjustment is not applicable to this study.

#### **6.6. Interim Analysis**

An interim analysis was planned in Protocols Amendment 06 and previous versions but was removed from Protocol Amendment 07. Therefore, no formal interim analysis will be conducted.

## 7. SUMMARY OF STUDY POPULATION DATA

### 7.1. Subject Disposition

The subject disposition will be summarized by treatment arm and overall for all randomized subjects. The summary will include the number of subjects in the ITT Population, the numbers and percentages of subjects in the Safety Population, FAS, PPS, PK Population and Biomarker Population. The summary will also include the numbers and percentages of completers and non-completers at Week 24 (Visit 11) and Week 32 (Visit 13), as well as the number and percentage of non-completers by primary discontinuation reason. The number of percentages of subjects enrolled prior to Protocol Amendment 06 and on/after Protocol Amendment 06 will also be provided.

### 7.2. Demographics and Baseline Characteristics

Subject demographics and baseline characteristics will be descriptively summarized for the FAS Population by planned treatment arm and overall, safety population by actual treatment and overall. Specifically, for subject demographics, the following variables will be summarized:

- Age at randomization (continuous and categorical: < 65 years or ≥ 65 years)
- Sex (categorical: Male or Female)
- Race (categorical: American Indian or Alaska Native, Asian, Black or African American, Native Hawaiian or Other Pacific Islander, White, or Other/Multiracial)
- Ethnicity (categorical: Hispanic/Latino or Not)
- Country (categorical: Philippine or US)

For baseline characteristics, the following variables will be summarized for study eye:

- Lesion type (PCV or non-PCV)
- Prior anti-VEGF treatment in the study eye (Yes or No)
  - If yes, refractory to anti-VEGF treatment or not (Yes or No)
  - And, how long since the first anti-VEGF treatment
  - And, the type of most recent prior anti-VEGF treatment (type 1: Lucentis or Ranibizumab; type 2: Avastin or Bevacizumab; type 3: Eylea or Aflibercept)
- Baseline BCVA
- Baseline FA readings including total lesion area, total area of CNV, and greatest linear dimension of the total lesion area
- Baseline CST, MV and CRLT
- Baseline IOP
- Baseline lens status (aphakic, pseudophakic or phakic)

Summaries of demographic and baseline characteristics will be repeated on the following subgroups:

- Country
- Lesion type (PCV or non-PCV)
- Prior anti-VEGF treatment in the study eye (Yes or No)
- Protocol version (before Amendment 06 or on/after Amendment 06)

### **7.3. Medical and Surgical History**

For this study, medical and surgical history (i.e., medical events) will be coded using MedDRA 20.0, 2017. Each medical event will be classified into a SOC and mapped to a PT.

The medical and surgical history will be summarized for the FAS population. Subjects reporting any medical and surgical history at baseline will be tabulated by SOC and PT for each planned treatment and overall.

### **7.4. Protocol Deviations**

In this study, protocol deviations are categorized as follows:

- Safety issues
- Consent issues
- Enrollment issues
- Protocol implementation issues
- Other deviations

A protocol deviation is considered major if it may affect the subject's rights, safety, or well-being and/or the completeness, accuracy, and reliability of the study data. Santen's study team will review all protocol deviations and determine the list of major protocol deviations prior to database lock. All randomized subjects with any major protocol deviation(s) will be tabulated by deviation category for each planned treatment and overall. In addition, all protocol deviations will also be listed.

### **7.5. Prior and Concomitant Medications**

For this study, non-study medications, including prior and concomitant medications, will be coded using World Health Organization Drug Dictionary Enhanced (WHO-DDE) (March 2017). Each non-study medication will be classified using the Anatomical-Therapeutic-Chemical (ATC) classification system and mapped to a WHO-DDE preferred drug name.

Non-study medications will be summarized for the Safety population. Subjects taking any prior medications will be tabulated by ATC level 3, level 4 and preferred drug name for each actual treatment received and overall. A subject will be counted at most once for each prior medication, even if the subject took the same prior medication on multiple occasions. Subjects taking any concomitant medications will be tabulated similarly. In addition, prior medications and concomitant medications will also be listed, separately.

Any prior medications taken for target disease will be summarized and listed.

### **7.6. Exposure to Study Medication**

The treatment exposure to DE-122 will be reflected by the number of DE-122 injections received (1 to 6). For Safety subjects, the exposure will be summarized by frequency and percentage for actual treatment received and overall.

### **7.7. Treatment Compliance**

A subject will be considered fully compliant if the study eye was injected with the planned treatment at each visit when the injection is scheduled per protocol. If the subject skipped the injection of DE-122 at the investigator's decision with the corresponding AE reported, then this subject will still be considered as treatment compliant. Treatment compliance will be summarized for the FAS population by planned treatment and overall. The treatment compliance statuses will also be listed by planned treatment, subject ID, and injection visit.

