7.5.2.4. Visit 4 (Week 4 (D29±3))

- Perform the following assessments: (all ophthalmic procedures to be performed OU)
 - Query for AEs
 - Update medical history and medications
 - Vital signs
 - BCVA (ETDRS)
 - M-CHARTS™
 - Slit-lamp biomicroscopy
 - IOP
 - Indirect ophthalmoscopy
 - SD-OCT
 - SS-OCT angiography (for selected sites)
 - Fundus photography
 - Fluorescein angiography
- Collect urine and blood specimen for the following examinations:
 - Urinalysis
 - Hematology, chemistry serum sample
 - PK serum sample (**for only the subjects who have consented under the protocol prior to Version 4.0**)
 - Biomarker serum sample
- **Perform Lucentis® administration** as per drug labeling, and then perform the following procedures after Lucentis® administration.
 - IOP will be measured at 40 (± 10) minutes post-injection.
 - If post-injection IOP is ≤ 21 mmHg AND increased < 10 mmHg from pre-injection IOP and there is no concern regarding retinal artery perfusion, DE-122 or Sham IVT will be administered.
 - If post-injection IOP is > 21 mmHg OR increased ≥ 10 mmHg from pre-injection IOP, IOP measurement will be repeated at 60 (± 10) minutes post-injection.
 - IOP will be measured at 60 (± 10) minutes post-injection, if applicable.
 - If post-injection IOP at 60 (± 10) minutes is ≤ 21 mmHg AND increased < 10 mmHg from pre-injection IOP and there is no concern regarding retinal artery perfusion, DE-122 or Sham IVT will be administered.

- If post-injection IOP at 60 (± 10) minutes is > 21 mmHg, however the IOP is < 30 mmHg AND increased < 10 mmHg from pre-injection IOP and there is no concern regarding retinal artery perfusion, DE-122 or Sham IVT will be administered per the Clinical Investigator's discretion.
If the Clinical Investigator determine that DE-122 or Sham IVT will Not be administered, the subject will be treated according to the Clinical Investigator's discretion.
- **If post-injection IOP at 60 (± 10) minutes is ≥ 30 mmHg OR increased ≥ 10 mmHg from pre-injection IOP, DE-122 or Sham IVT should not be administered.** The subject should be prescribed a topical IOP-lowering medication until he or she returns for follow-up per the Clinical Investigator's discretion (an unscheduled visit may apply), and the event will be reported as an AE.
- **Perform DE-122 or Sham administration**, and then perform the following procedures after DE-122 or Sham administration.

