9.3. Treatment Compliance

In order to obtain efficacy and safety data, it is critical that the treatment regimen and visit schedule specified in this protocol are followed. The Clinical Investigator is required to administer the DE-122 injection and Lucentis®, and is responsible for scheduling the subject for follow-up visits as specified in the protocol. Study monitors will verify pertinent data to confirm the study is conducted according to the protocol.

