16.2.2. Statistical Hypotheses and Level of Significance

No statistical hypothesis is defined for this study.

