**Figure 1: Study Design Diagram**

### 3.2. Randomization and Masking

In Stage 1, the first 6 subjects will be randomized to either Arm 1 or Arm 2 in a 1:1 ratio. A blocked randomization with a fixed block size of 2 will be employed.

In Stage 2, approximately 70 subjects will be randomized to all three Arms in a 1:2:2 ratios. A blocked randomization with a fixed block size of 5 stratified by lesion type (polypoidal choroidal vasculopathy [PCV] vs. non-PCV) will be employed. Approximately one third (1/3) of the subjects in each arm are expected to have PCV in Stage 2.

This is a double-masked study, where the subjects and the examiners including the Principal Investigator (PI), are masked to the treatment regimen. However, the designated injecting physician (who is not the PI) will not be masked to the treatment regimen.

The Sponsor will have masked and unmasked data review teams. The designated Safety Review Team will review the safety data of the 6 subjects in Stage 1 to determine if the safety and tolerability of the doses at Week 4 are acceptable. In case of a medical emergency, the Principal

Investigator or site staff may reveal the treatment information by unmasking in the Interactive Web Response Systems (IWRS).

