### **3.3. Sample Size Planning**

Approximately 76 subjects (Arm 1: 17, Arm 2: 31, Arm 3: 28) with wet AMD will be enrolled at approximately 14 sites. The sample size is not based upon any statistical considerations.

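### SAP 7.7 excuses a skipped DE-122 injection but does not name Sham, so the by-arm compliance table can differ by definition alone; no exposure table counts scheduled Lucentis

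*SAP*

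**What the plan says.** SAP 7.7 has a base test and an exception. The base test is that the study eye received the planned treatment at each scheduled injection visit; a subject who meets it is fully compliant. The exception covers a DE-122 injection skipped at the investigator's "decision with the corresponding AE reported, then this subject will still be considered as treatment compliant". Compliance is then summarised for the Full Analysis Set by planned arm, with a listing by subject and injection visit.

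The protocol's injection-visit sections (7.5.2.1 and 7.5.2.4 to 7.5.2.8) measure intraocular pressure after Lucentis and before the second procedure. Above the stated limits at 60 minutes, "DE-122 or Sham IVT should not be administered" (Week 4; Weeks 8 to 16 read the same, and Day 1 and Week 20 carry close variants). A middle pressure range leaves the second procedure to the investigator's discretion. Both branches name DE-122 and Sham together. Protocol 9.3 says that "it is critical that the treatment regimen and visit schedule specified in this protocol are followed".

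On exposure, SAP 7.6 says: "The treatment exposure to DE-122 will be reflected by the number of DE-122 injections received (1 to 6"). It tabulates this for Safety subjects by actual treatment received. SAP 5.3 names both DE-122 and Lucentis as study medication, and Protocol 10.1.2 gives Lucentis in all groups.

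**The concern.** The pressure check comes after Lucentis and before the second procedure, so a hold can occur in any arm. The protocol treats it identically in all three arms; SAP 7.7, as worded, does not. A table meant to show whether the arms were treated as planned would then contain a difference that comes from its own definition, in the direction that favours the DE-122 arms.

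The exposure section adds a smaller gap. The trial compares DE-122 plus Lucentis with Lucentis alone, so a reader will want the number of Lucentis injections given in each arm. No summary in the SAP counts them. SAP 7.5 covers non-study medications only, SAP 9.5 covers rescue only, and the days-on-treatment variable in SAP 4.1.6 is defined but assigned to no table.

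**Working it through.** **Inputs.** The point concerns definitions, so no power figure is involved: Protocol 16.2.2 states "No statistical hypothesis is defined for this study" and SAP 3.3 states "The sample size is not based upon any statistical considerations". The denominators come from SAP 3.3: "Approximately 76 subjects (Arm 1: 17, Arm 2: 31, Arm 3: 28) with wet AMD will be enrolled".

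**Reproducing the arm sizes.** In Stage 1, "the first 6 subjects will be randomized to either Arm 1 or Arm 2 in a 1:1 ratio", giving 3/3/0. Stage 2 has about 70 subjects at 1:2:2, giving 14/28/28. The sum is 17/31/28 = 76, which matches. Injection visits are Day 1 and Weeks 4, 8, 12, 16 and 20, so six per subject.

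**The same event under both documents.** Take a subject with one mandatory hold after Lucentis and the adverse event reported.

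| | Protocol | SAP 7.7, read literally |
|---|---|---|
| Arm 1 (Sham) | second procedure withheld, AE reported | base test failed, exception does not name Sham: non-compliant |
| Arms 2 and 3 (DE-122) | second procedure withheld, AE reported | base test failed, exception applies: compliant |

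This takes a mandatory hold to be at the investigator's decision. The SAP does not say so, but the mandatory branch is the one in which the protocol calls for an AE. The discretionary branch does not require one, so a discretionary skip without an AE is not excused in any arm.

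**Size of one subject.** One such skip changes Arm 1 by 1/17 = 5.9 points. The same event changes Arms 2 and 3 by 0. Without the exception it would change them by 1/31 = 3.2 and 1/28 = 3.6 points.

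**Why the overall gap cannot be sized.** Let q be the probability of a skip at a visit and f the share of skips with an AE reported, both equal across arms and independent between visits. The documents give neither.

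- Arm 1 non-compliant: 1 − (1 − q)^6
- Arms 2 and 3 non-compliant: 1 − (1 − q(1 − f))^6

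| q (assumed) | Arm 1 | Gap, f = 100% | Gap, f = 50% | Gap, f = 0 |
|---|---|---|---|---|
| 1% | 5.9% | 5.9 | 2.9 | 0 |
| 2% | 11.4% | 11.4 | 5.6 | 0 |
| 5% | 26.5% | 26.5 | 12.4 | 0 |

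Gaps are in percentage points. The table shows only how strongly the answer depends on two unknowns. If the exception named Sham as well, both formulas would be the same and the gap would be 0 for every q and f.

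**The case against.** The strongest reply is that DE-122 is drafting shorthand for the second procedure. SAP 9.4 plans the post-injection pressure analyses for Lucentis and DE-122, although Table 5 of the SAP applies the procedure to Sham too. Protocol 9.3 requires the DE-122 injection and Lucentis to be given, in a trial with a Sham arm. That a skipped Sham fails the test is therefore an inference from silence. This stands as a reason for caution about intent. It does not settle the wording, because the SAP names DE-122 and Sham together in other places (the Table 1 footnotes and Table 5).

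A reader might also infer more than the documents support:

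- **That the compliance gap is some 6 to 26 points.** This needs an unsourced q, an AE for every hold and independence between visits. The discretionary branch requires no AE. At Week 20 a held injection can still be given within the visit window, so a hold is not always a skip. Clustering of holds within subjects would reduce the share with at least one.
- **That a subject held repeatedly is reported as fully compliant, with the doses missed hidden.** SAP 7.7 keeps the term fully compliant for subjects treated at every scheduled visit; excused subjects are called treatment compliant. SAP 7.6 tabulates the number of DE-122 injections received, so a subject given one dose appears as one.
- **That the range 1 to 6 is an error for lack of a zero.** The table is by actual treatment received. A subject never given DE-122 may fall outside the DE-122 groups, though the SAP does not define that classification.
- **That missed Lucentis goes unseen.** A missed Lucentis dose fails the base test and could show in the by-visit listing. The hold comes after Lucentis, so it does not itself remove that visit's dose, and the documents suggest no mechanism for an imbalance.
- **That efficacy results are affected.** The primary analysis uses the Full Analysis Set by planned arm (SAP 8 and 8.1.1). The Per-Protocol Set rests on review of protocol deviations (SAP 5.4). The skipped-injection analyses (SAP 8.1.2 and 8.2.2) refer to any scheduled injection.

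**Conclusion.** The point holds as a minor inconsistency. The exception in SAP 7.7 is narrower than the protocol rule it reflects, and, followed literally, it gives different compliance results for the same event in different arms. The supportable size is 5.9 points of Arm 1 compliance for each Sham subject with such a skip. No overall gap can be stated. If the authors meant DE-122 or Sham, the asymmetry is one of wording only, but the text should say so.

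The missing Lucentis count is a useful addition and not an error: SAP 5.3 treats Lucentis as study medication, and a reader comparing combination with monotherapy would expect to see it. The consequences are confined to the compliance and exposure tables.

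**What to change.** 1. In SAP 7.7, word the exception as DE-122 or Sham, and say whether it covers mandatory holds, discretionary holds or both.
2. Report protocol-directed holds as their own category in every arm, separate from subjects who received all scheduled injections.
3. In SAP 7.6, tabulate by arm the number of Lucentis injections and the number of DE-122 or Sham injections received, each from 0 to 6.

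The cost is a few words and some table rows, drawn from injection records that the by-visit compliance listing already needs. The DE-122 compliance rate may look slightly lower once excused holds are shown separately. The clinical withholding rule is not in question, and no change to it is proposed.

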## **8. EFFICACY ANALYSES**

Unless specified otherwise, the efficacy analyses will be performed on the FAS, where subjects are classified by planned treatment, irrespective of the actual treatment received.

Unless specified otherwise, all efficacy analyses will be performed on the study eye, and the data on fellow eye will not be used.

### **8.1. Primary Endpoint**

#### **8.1.1. Primary Analysis**

The primary efficacy endpoint is mean change from baseline in BCVA at Week 24. No formal statistical hypothesis testing will be implemented for the primary endpoint. Descriptive summaries will be provided by each planned treatment arm. The differences in mean change between Arm 2 or 3 and Arm 1, as well as the corresponding 95% confidence intervals based on t-test without multiplicity adjustment will also be provided. Descriptive summaries of BCVA measured at Week 28 and Week 32 will be provided, in which any records after the rescue injection(s) will be censored.

The primary analyses will be performed on the FAS. Besides the summary tables, plots of BCVA measures versus analysis visit will be provided. BCVA score, and percent change from baseline will also be summarized.

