### 3. STUDY DESIGN

#### 3.1. General Study Design

This is a randomized, double masked and active controlled study assessing the safety and efficacy of repeated intravitreal injections of DE-122 (2.0 mg or 4.0 mg) in combination with Lucentis® compared to Lucentis® monotherapy in subjects with wet AMD. Seventy-six (76) subjects with wet AMD were randomly assigned to one of three treatment arms in two stages:

[figure not shown]
- Arm 1: Sham + Lucentis® 0.5 mg (N=17)
- Arm 2: DE-122, 2.0 mg + Lucentis® 0.5 mg (N=31)
- Arm 3: DE-122, 4.0 mg + Lucentis® 0.5 mg (N=28)

As shown in the Study Design Diagram ([Figure 1](#)), this study will consist of two stages. In Stage 1, the first 6 subjects will be randomized to either Arm 1 or Arm 2 in a 1:1 ratio. After all the 6 subjects have completed the Week 4 visit, the Safety Review Team will review the data to determine whether or not the safety and tolerability is acceptable. Subsequently in Stage 2, approximately 70 subjects will be randomized in a 1:2:2 ratios among the three arms.

Subjects will receive, in combination with Lucentis®, either 6 monthly intravitreal injections of DE-122 (2.0 mg), DE-122 (4.0 mg), or Sham in the study eye. The Primary Analysis is planned when all subjects complete the Week 24 visit. The Follow-up Analysis is planned at Week 32 to assess the number of anti-VEGF injections used for Rescue in addition to efficacy and safety data.

To be eligible, a subject must have been previously treated (i.e., At least 3 IVT injections of Anti-VEGF for treatment naïve eyes or eyes adequately maintained on continuous intravitreal anti-VEGF therapy). This condition was not required for subjects who enrolled before Protocol Amendment 06.

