### **8.3. Subgroup Analyses**

To assess the homogeneity of treatment effects among subgroups, primary endpoint will be analyzed for the following subgroups:

- Age group (< 65, or  $\geq$  65 years)
- Sex (males or females)
- Country (Philippine or US)
- Lesion type (PCV or non-PCV)
- Prior anti-VEGF treatment in the study eye (yes or no)
- Type of most recent prior anti-VEGF treatment in the study eye (type 1: Lucentis or Ranibizumab; type 2: Avastin or Bevacizumab; type 3: Eylea or Aflibercept)
- Protocol version (before or on/after Amendment 06)
- Lens status (phakic or non- phakic).

Other subgroup analyses may be performed as suggested by the data.

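### Three of the 17 planned controls for the 4.0 mg arm were randomised before that arm opened, and the SAP reports no concurrent-control difference

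*SAP*

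**What the plan says.** **Randomisation (SAP 3.1 and 3.2).** "In Stage 1, the first 6 subjects will be randomized to either Arm 1 or Arm 2 in a 1:1 ratio"; for that stage, "A blocked randomization with a fixed block size of 2 will be employed". Stage 2 comes later: "After all the 6 subjects have completed the Week 4 visit, the Safety Review Team will review the data". Protocol 7.4 makes enrolment into the three arms depend on that review. Then "In Stage 2, approximately 70 subjects will be randomized to all three Arms in a 1:2:2 ratios", and here "A blocked randomization with a fixed block size of 5 stratified by lesion type (polypoidal choroidal vasculopathy [PCV] vs. non-PCV) will be employed". The stages differ in arms, ratio, block size and stratification.

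**Analysis.** SAP 8.1.1 gives, on the Full Analysis Set, "The differences in mean change between Arm 2 or 3 and Arm 1", with t-based 95% intervals and no hypothesis test. SAP 8.2.1 plans the same differences for the secondary endpoints. The Full Analysis Set (SAP 5.3) is not divided by stage, and SAP 6.1 rules out covariate adjustment. The sensitivity analyses in 8.1.2 and 8.2.2 concern the per-protocol set, LOCF (BCVA only) and skipped injections. The subgroups in 8.3 include prior anti-VEGF treatment and protocol version, but not stage.

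**Entry rule.** On the requirement for previous anti-VEGF treatment, SAP 3.1 adds: "This condition was not required for subjects who enrolled before Protocol Amendment 06".

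**The concern.** A randomised comparison of Arm 3 with Arm 1 needs controls who could have been allocated to Arm 3. The Stage 1 controls could not, because that arm was not open. If Stage 1 and Stage 2 subjects differ in expected BCVA change, through calendar period, sites or case mix, the difference enters the 4.0 mg estimate as bias. The planned interval reflects sampling error only and does not show it.

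The two doses are also affected unequally. Arm 2 has Stage 1 subjects on its own side, which offset part of any shift in Arm 1; Arm 3 has none. Comparing each dose with Lucentis alone is part of the primary objective (Protocol 6, SAP 2.1).

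**Working it through.** **1. Reproduce the planned arm sizes.** Inputs: SAP 3.2 (stage sizes, ratios, blocks) and 3.3 (17/31/28, total 76).

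- Stage 1: 6 subjects at 1:1 in blocks of 2 = 3/3/0.
- Stage 2: 70 × (1/5, 2/5, 2/5) = 14/28/28.
- Sum: 17/31/28 = 76, an exact match. The stated sizes include the Stage 1 subjects, so pooling is the plan.

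**2. Stage 1 share of each arm.** Arm 1: 3/17 = 17.6%. Arm 2: 3/31 = 9.7%. Arm 3: 0/28 = 0%.

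**3. Shift in the pooled differences.** Let Stage 1 subjects change by D letters more than Stage 2 subjects, whatever the treatment. Then

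shift = D × (Stage 1 share of the DE-122 arm − Stage 1 share of Arm 1).

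- Arm 3 − Arm 1: D × (0 − 0.176) = −0.176D.
- Arm 2 − Arm 1: D × (0.097 − 0.176) = −0.080D.

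| Assumed D (letters) | Arm 3 − Arm 1 | Arm 2 − Arm 1 |
|---|---|---|
| 2 | −0.35 | −0.16 |
| 5 | −0.88 | −0.40 |
| 10 | −1.76 | −0.80 |
| 15 | −2.65 | −1.20 |

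With positive D, pooling understates the DE-122 effect; with negative D it overstates it.

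**4. Cost of using concurrent controls for Arm 3 − Arm 1.** Half-width = t(0.975, n1 + n2 − 2) × SD × √(1/n1 + 1/n2). The documents give no SD, so a range is shown.

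| Assumed SD (letters) | Pooled, 28 vs 17 | Stage 2 only, 28 vs 14 |
|---|---|---|
| 8 | 4.96 | 5.29 |
| 10 | 6.20 | 6.62 |
| 12 | 7.44 | 7.94 |
| 15 | 9.30 | 9.92 |

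Standard error ratio: √(1/14 + 1/28) / √(1/17 + 1/28) = 1.065. Half-width ratio, with 40 and 43 degrees of freedom: 1.067. The largest shift in step 3 (2.65 letters) is below the smallest pooled half-width (4.96).

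**5. Bias against variance for Arm 3 − Arm 1.** In units of SD², the variance is 1/17 + 1/28 = 0.0945 pooled and 1/14 + 1/28 = 0.1071 concurrent-only. Squared bias of the pooled estimate is 0.176² × D² = 0.0311D². The two mean squared errors are equal when D²/SD² = (0.1071 − 0.0945)/0.0311, so |D| is about 0.64 SD: 5.1, 6.4, 7.6 and 9.5 letters at SD 8, 10, 12 and 15. Below that, pooling has the lower mean squared error.

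**6. Arm 2 − Arm 1 within stage.** Variance factors: Stage 1, 1/3 + 1/3 = 0.667; Stage 2, 1/14 + 1/28 = 0.107. Inverse-variance combination: 1/(1/0.667 + 1/0.107) = 0.0923, standard error factor 0.3038. Pooled: √(1/17 + 1/31) = 0.3018. The ratio is 1.007, and all 48 subjects are kept.

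**The case against.** **The study is descriptive, unpowered and without a hypothesis, and the possible bias is smaller than the sampling error.** This stands and limits the weight of the point. It does not make the concurrent difference uninformative, since the SAP does report differences with intervals.

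**Dropping three controls may make the estimate worse.** This also stands. By step 5, pooling has the lower mean squared error unless |D| exceeds about 0.64 SD. A reader might infer that the pooled Arm 3 difference must be replaced. With no D or SD in the documents that cannot be shown; reporting both can be justified.

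**The SAP already looks at the likely source of a stage difference.** In part. SAP 7.1 and 7.2 count subjects by amendment and repeat baseline summaries by prior treatment and protocol version, and 8.3 analyses the primary endpoint by both. If all Stage 1 subjects entered before Amendment 06, the on/after subgroup holds only Stage 2 subjects and is concurrent. But it then leaves out any Stage 2 subject enrolled before the amendment. The prior-treatment subgroup splits on treatment history, not stage. Section 8.3 promises no between-arm intervals and covers the primary endpoint only.

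**The three controls need not have entered under other rules.** This stands. A reader might infer that they are known to have entered without the prior-treatment requirement, and may be treatment-naive. As the first subjects enrolled they probably did precede Amendment 06, but neither document dates that amendment or states the protocol version for Stage 1. The rule change is tied to the amendment, so Stage 2 subjects may also have entered under the earlier rule. Non-concurrency does not depend on this inference.

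**Conclusion.** The point holds as a cheap improvement. In Arm 3 minus Arm 1, 3 of the 17 planned controls (17.6%) are not protected by randomisation, and no planned analysis isolates the full concurrent comparison. The shift is −0.18D, for example −0.9 letters at D = 5 and −1.8 at D = 10, against pooled half-widths of about 5 to 9 letters at SDs of 8 to 15.

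A reader might take both dose comparisons to use non-concurrent controls. They do not: Stage 1 randomised Arm 1 against Arm 2, so for that contrast its subjects are concurrent. The only defect there is pooling across 1:1 and 1:2 allocation without accounting for stage, worth −0.08D.

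These figures rest on planned numbers (Week 24 counts may be lower), equal SDs across arms, and a stage difference that is the same under every treatment. D and SD are assumptions, and the documents give no sign for D.

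**What to change.** In SAP 8.1.1 and 8.2.1:

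- Beside the pooled Arm 3 minus Arm 1 difference, report the same difference and 95% interval in Stage 2 subjects only (planned 28 vs 14).
- Compute Arm 2 minus Arm 1 within each stage and combine the two estimates, with the weighting stated in advance.
- Keep Stage 1 subjects in all by-arm and safety summaries.

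It would also help to tabulate the Stage 1 subjects by protocol version in SAP 7.1, which would settle the entry-rule question.

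The cost is SAP wording and one extra table, with an interval about 7% wider for the added Arm 3 contrast and a standard error about 0.7% higher for Arm 2. No new data are needed.
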